In the first part of the study, we will make a determination of the laser irradiance that will be tolerated by all study subjects (as measured by lack of discomfort over the whole 1 minute exposure). Each subject will receive up to five initial one-minute treatments at 1, 2, 3, 4, and 5 W/cm² (0.2, 0.4, 0.6, 0.8 and 1 Watt). If a subject experiences discomfort at any of these irradiances, a second set of exposures will be made between the highest tolerable irradiance and the one that was not tolerable. These will be done at 0.2 W/cm² increments (e.g., 3.2, 3.4, 3.6, and 3.8 W/cm²). The highest irradiance the subject tolerates for 1 minute will be identified as that subject's maximum tolerable irradiance. After all subjects are tested, we will select the highest irradiance that was tolerated by all ten subjects and use this in the second phase of the study. The determination of the maximum tolerable irradiance of all 10 subjects will be determined before starting the second phase of the study below.

Within 6 months after the first test exposures and determination of the universal maximum tolerable irradiance, each subject will receive a one minute laser treatment at the maximum tolerable irradiance. Four hours later, we will take two 4 mm punch biopsies from bilateral areas of the lower back. One biopsy will be taken from the skin area treated by the laser, and one from an untreated area on the other side of the back as a control. Each biopsy sample will be divided into two using a sterile scalpel. One half of each sample will be immersed in formalin and shipped to the Massachusetts General Hospital Dept. of Dermatopathology for processing, fixing, and embedding in paraffin for determination of specific immune cell populations using specific immunohistochemical staining. The samples will also be stained with Hematoxylin and Eosin for histology at Massachusetts General Hospital Dept. of Dermatopathology. The other half of each sample will be flash frozen at -80° C for subsequent qPCR to identify upregulation of specific cytokines and chemokines such as IL-1a, IL-1b, TNFa, CCL2, CCL6, CCL11, CCL17, CCL19, CCL20, and CCR7. After flash freezing, this tissue will be sent to the Massachusetts General Hospital Vaccine and Immunotherapy Center for processing.

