Prior to all laser treatments, female patients of childbearing age will be administered a urine Beta hCG urine test. A positive result will disqualify the patient from the study. These results will be intended for research purposes only and will not be included in the patients' medical record.

A 95% water polymer gel will be applied prior to all laser treatments to all laser-exposed skin in order to limit excessive heat buildup within the skin. The gel will also be applied to the control site non-treated skin that will be biopsied. Subjects and research personnel will wear protective goggles appropriate to the safety rating of the laser.

In order to determine the maximum tolerable laser irradiance to be used in the biopsy phase of the study, each subject will receive a series of 1 minute exposures on 5 mm² areas of the skin of the lower back from continuous wave 1064 nm laser light emitted by a modified handheld diode laser device (IPG Photonics). Prior to these treatments, subjects will be informed about the kind of skin sensations the laser may cause and will always be asked to indicate to the study doctor when the exposure becomes uncomfortable. In the case that an exposure produces discomfort in the subject (a tingling or pinprick sensation or uncomfortable feeling of hotness), the exposure will be terminated. After the completion of each test site, the study personnel will examine the skin surface for signs of damage or alteration. Digital photographs will be taken of all sites before and after laser treatment.

Up to five initial one-minute treatments will be given to each subject starting at 1 W/cm² and increasing at 1 W/cm² increments up to a maximum of 5 W/cm² (0.2, 0.4, 0.6, 0.8 and 1 Watt). If a subject experiences discomfort during any of these treatments, a second set of treatments will be made between the highest tolerable irradiance and the one that was not tolerable. These will be done at 0.2 W/cm² increments (e.g., 3.2, 3.4, 3.6, and 3.8 W/cm²). The highest irradiance the subject tolerates for 1 minute will be identified as that subject's maximum tolerable irradiance. After all subjects are tested, we will select the highest irradiance that is tolerated by all ten subjects and use this in the second phase of the study.

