The estimated mean density of CD11c+ dermal dendritic cells in the dermal layer has been described in a published study of 15 normal healthy volunteers as being 73 cells per mm skin section (Zaba LC, Fuentes-Duculan J, Steinman RM, Krueger JG, Lowes MA. Normal human dermis contains distinct populations of CD11c+BDCA-1+ dendritic cells and CD163+FXIIIA+ macrophages. J Clin Invest. 2007 Sep;117(9):2517-25.). The standard mean error was approximately ±10 cells. The study on effect of 1064 nm laser on dermal dendritic cells using the C57BL/6 mouse model showed that a one minute exposure to 1064 nm laser light at 5 W/cm² generated a net change in estimated numbers of CD11c+ dermal dendritic cells in the dermis of about 108% at 6 hours post exposure (Kashiwagi et al.).

Using a power calculation to provide a p value of 0.05 at a minimum of 80% power and a standard deviation of differences of 1.0, nine subjects would be required to see similar changes in cell density. We therefore conclude that ten subjects will be sufficient to see similar statistically-significant changes in human skin that were observed in the mouse skin.

All power analyses, datasets and statistical analyses will be independently performed on datasets by [name], Ph.D., an expert statistician of the Department of Medicine at the University of California, Irvine.

SECTION 4: SUBJECTS (PERSONS/CHARTS/RECORDS/SPECIMENS)

A. Number of Subjects (Charts/Records/Biospecimens)

- 1. Indicate the **maximum number of subjects to be recruited/consented** on this UCI protocol. This is the number of potential subjects you may need to recruit to obtain your target sample size. This number should include projected **screen failures and early withdrawals**. **Note:** The IRB considers individuals who sign the consent form to be "enrolled" in the research.
- 2. For Mail/Internet surveys include the number of people directly solicited.
- 3. If the study involves use of **existing charts, records, biospecimens**, specify the maximum number that will be reviewed/tested to compile the data or the sample population necessary to address the research question.

The maximum number of subjects to be consented is 15 subjects.

4. Of the maximum number of subjects listed above, indicate the target sample size for the study. This

- is the number of subjects expected to complete the study or the number necessary to address the research question.

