- 5. For social/behavioral research, the maximum sample size is often similar to the target sample size. If the **maximum sample size** is significantly greater (i.e., ≥ 1.5x) than the **target sample size** provide a justification.
- 6. For studies where multiple groups of subjects will be evaluated, **provide a breakdown per group** (e.g. controls vs. experimental subjects; children vs. adults; by age group).

The target sample size is 10 subjects.

- 7. For **multi-center research**, indicate the overall sample size for the entire study (across all sites).
- [X] Not applicable This study is not a multi-center research study.
- 8. Demonstrate that the **target sample size will be sufficient** to achieve the study goal and should coincide with the statistical approach **described in Section 3B**. *Note:* Required for scientific review.
- 9. **Sources and information** of assumed group effects and variability should be supplied (e.g., pilot data; data from related literature). *Note:* Required for scientific review.

Quantitative analysis will pertain to changes in the density of CD11c+ dermal dendritic cells in the laser-treated skin as compared with non-laser treated control skin. For assessment of statistical significance, we will apply a paired sample t-test.

The estimated mean density of CD11c+ dermal dendritic cells in the dermal layer has been described in a published study of 15 normal healthy volunteers as being 73 cells per mm skin section (Zaba LC, Fuentes-Duculan J, Steinman RM, Krueger JG, Lowes MA. Normal human dermis contains distinct populations of CD11c+BDCA-1+ dendritic cells and CD163+FXIIIA+ macrophages. J Clin Invest. 2007 Sep;117(9):2517-25.). The standard mean error was approximately ±10 cells. The study on effect of 1064 nm laser on dermal dendritic cells using the C57BL/6 mouse model showed that a one minute exposure to 1064 nm laser light at 5 W/cm² generated a net change in estimated numbers of CD11c+ dermal dendritic cells in the dermis of about 108% at 6 hours post exposure (Kashiwagi et al.).

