Using a power calculation to provide a p value of 0.05 at a minimum of 80% power and a standard deviation of differences of 1.0, nine subjects would be required to see similar changes in cell density. In the event that the standard deviation of differences is 0, only two subjects would be needed. We therefore conclude that ten subjects will be sufficient to see similar statistically-significant changes in human skin that were observed in the mouse skin.

B. Inclusion and Exclusion Criteria

- 1. Describe the **characteristics and provide justification** for inclusion of the proposed subject population. At a minimum include information about the age and gender of the study population.
- 2. Describe **different subject groups** (e.g., students and teachers; control group and treatment group(s), children and adults) separately.

This study is targeted at healthy adults ages 18-50. We will recruit subjects affiliated with the Beckman Laser Institute or Department of Dermatology including our own patients as well as students and

employees affiliated with the Beckman Laser Center. This will be a single-site pilot study.

We do not anticipate potential barriers to accrual due to the small number of subjects needed and the large pool of potential subjects. There are no other restrictions of race, ethnicity or sex.

- 3. Provide the **inclusion and/or exclusion criteria** for the proposed subject population, as applicable.
- [] Not applicable This is not a clinical investigation and/or the characteristics of the population sufficiently describe the proposed subject population.

Inclusion Criteria

- Healthy men or women ages 18-50
- Fitzpatrick skin phototypes I and II
- Able and willing to comply with all visit, treatment and evaluation schedules and requirements
- Able to understand and provide written informed consent

Exclusion Criteria

- Use of systemic steroids or use of topical steroids on the back within 30 days prior to study
- Use of tanning solutions on the back within 48 hours prior to study
- History of hemophilia or clotting disorders or current use of an anticoagulant
- Mentally incompetent, prisoner, or evidence of alcohol or drug impairment
- History of immunosuppressive or immune deficiency disorders, including human immunodeficiency virus (HIV), acquired immunodeficiency syndrome (AIDS), or the use of immunosuppressive medications.
- Abnormal photosensitivity

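### Does the unexplained SD of differences of 1.0 undermine the sample size of ten?

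*Combined protocol and SAP*

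**What the plan says.** Section 3B (Statistical Plan and Data Analysis) gives the whole sample-size argument, and Section 4A (Number of Subjects) repeats it. The test is a paired t-test on CD11c+ dermal dendritic cell density, with one laser-treated and one control biopsy per subject.

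- **Human control data:** a mean of 73 cells per mm of skin section in 15 healthy volunteers, with this precision: "The standard mean error was approximately ±10 cells".
- **Planning effect, from mice at 5 W/cm²:** "a net change in estimated numbers of CD11c+ dermal dendritic cells in the dermis of about 108% at 6 hours post exposure".
- **Calculation:** p value 0.05, at least 80% power, and "a standard deviation of differences of 1.0, nine subjects would be required to see similar changes in cell density".
- **Conclusion:** "ten subjects will be sufficient to see similar statistically-significant changes in human skin that were observed in the mouse skin".

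Section 4A adds one further scenario: "In the event that the standard deviation of differences is 0, only two subjects would be needed". Item 9 of the form, also in Section 4A, asks that sources "of assumed group effects and variability should be supplied (e.g., pilot data; data from related literature" and so on.

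Two features of the conduct bear on whether the mouse effect carries over. On irradiance, the Laser Treatment section says: "we will select the highest irradiance that is tolerated by all ten subjects and use this in the second phase of the study", with test exposures going no higher than 5 W/cm². On timing, Section 1 says: "Four hours later, we will take two 4 mm punch biopsies from bilateral areas of the lower back".

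**The concern.** An SD of differences of 1.0 follows directly after figures in cells per mm, yet it cannot be in that unit. At 1.0 cell/mm, a rise of about 79 cells/mm would be a standardised effect of about 79, and two subjects would be enough. The reader has to work out the unit. The sidedness must be inferred too: a one-sided test would need only seven subjects.

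The cited standard error implies a human SD, but that SD is never used. Getting from it to an SD of differences also needs a treated-site SD and a within-person correlation, and the documents give neither. Form item 9 is therefore only partly answered: the effect has a source, the variability of the difference does not.

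The effect is borrowed from mice at one irradiance and at 6 hours, whereas the human biopsies come at 4 hours and at an irradiance not yet known. No detectable difference in human skin is stated, and the only alternative scenario (SD of 0) is a degenerate limit. If 1.0 were optimistic, or the human effect smaller, each subject would have two biopsies in a study less able to show an effect than its justification suggests.

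**Working it through.** **Inputs from the documents.** Control mean 73 cells/mm; standard error about 10 in 15 volunteers; effect 108%; SD of differences 1.0; alpha 0.05; target of ten. **Assumptions, not in the documents.** The standard error is that of the mean over all 15 volunteers; within-person correlation ρ runs from 0 to 0.75; the treated-site SD either equals the control SD or grows in proportion to its mean.

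**Method.** Power of the paired t-test from the noncentral t distribution, with n − 1 degrees of freedom and noncentrality d√n, where d = mean difference / SD of differences.

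**1. The plan's own figure.** Read both quantities as multiples of the control mean: d = 1.08 / 1.0 = 1.08.

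| n | Two-sided power | One-sided power |
|---|---|---|
| 7 | 66.6% | 80.8% |
| 8 | 74.6% | 86.4% |
| 9 | 80.9% | 90.4% |
| 10 | 85.9% | 93.3% |

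Nine is the smallest n reaching 80% in the two-sided test. The answer thus identifies the reading: two-sided, with an SD of differences of 1.0 × 73 = 73 cells/mm. The normal approximation gives seven, so the t distribution was used.

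**2. What the cited standard error implies.** Control SD = 10 × √15 = 38.7 cells/mm, and 38.7 / 73 = 0.53 of the mean. The planned rise is 1.08 × 73 = 78.8 cells/mm.

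*Equal SDs at both sites:* SD of differences = 38.7 × √(2(1 − ρ)).

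*Treated SD proportional to its mean:* treated SD = 38.7 × 2.08 = 80.6, and SD of differences = √(38.7² + 80.6² − 2ρ × 38.7 × 80.6).

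| Case | ρ | SD of differences, cells/mm | As multiple of 73 | Power at ten for a 108% rise | Rise with 80% power at ten |
|---|---|---|---|---|---|
| Equal | 0 | 54.8 | 0.75 | 98.1% | 75% |
| Equal | 0.25 | 47.4 | 0.65 | 99.6% | 65% |
| Equal | 0.5 | 38.7 | 0.53 | >99.9% | 53% |
| Proportional | 0 | 89.4 | 1.22 | 70.0% | 135% |
| Proportional | 0.25 | 80.2 | 1.10 | 79.0% | 111% |
| Proportional | 0.5 | 69.8 | 0.96 | 88.7% | 85% |
| Proportional | 0.75 | 57.5 | 0.79 | 97.0% | 55% |

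In the proportional case the last column lets the treated SD follow the rise being detected.

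**3. Where ten stops being enough.** The smallest d with 80% power at n = 10 is 0.996. Ten pairs therefore hold 80% power for the planned rise up to an SD of differences of 78.8 / 0.996 = 79.2 cells/mm, or 1.08 of the mean. With equal SDs this is not exceeded at any ρ ≥ 0. With proportional SDs it is exceeded only when ρ is below about 0.28. The plan's 1.0 is reproduced by the proportional case at ρ of about 0.43, so it is not at odds with the cited standard error.

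**4. If the human effect is smaller.** At the plan's SD, ten pairs have 80% power for a rise of 0.996 × 73 = 72.7 cells/mm, about 100% of control or 92% of the mouse effect (0.996 / 1.08). Power is 63% for three quarters of the mouse effect and 33% for half of it. With equal SDs, the detectable rise of 53% to 75% is about half to 70% of the mouse effect.

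**The case for a change.** The best case for a change is that this is the only justification for the number of subjects, that the form expressly asks for the source of the variability, and that the repair would be one paragraph in two places. Calling the study a pilot does not fully answer this, because its stated aim is a significant increase and it claims that ten will be enough. At the plan's own SD that claim has little slack: half the mouse effect would need 29 subjects.

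Part of this stands. The unit, source and sidedness are missing, and the SD of 0 sentence tells the reader nothing.

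The rest does not lead to a change. The sufficiency claim is already limited to changes similar to those in mice, and Section 1 makes similarity to mice the hypothesis under test. The species, irradiance and time behind the 108% are stated openly, although the 4-hour against 6-hour difference and the unknown irradiance draw no comment. Recalculating after the tolerance phase would add nothing, since that phase takes no biopsies and yields no cell densities. A detectable rise follows from the plan's own inputs in one line, and a statistician would report the mean paired difference with its confidence interval as a matter of course.

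**Conclusion.** No change follows. This is a gap in documentation that a statistician can fill from the plan itself: only a two-sided paired t-test with both quantities on the scale of the control mean gives nine. The calculation is correct, and ten pairs give 85.9% power on the plan's inputs.

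The documents cannot settle whether 1.0 is cautious or optimistic. With equal SDs it is cautious, against 0.53 to 0.75 for correlations of 0.5 to 0. The less favourable case needs both a treated-site SD rising in proportion to its mean and a correlation below about 0.28 between two sites on the same person's back. Even then, power for the planned effect falls no lower than 70% for non-negative correlations. Neither condition has support in the documents.

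These figures rest on reading the cited error as the standard error over all 15 volunteers and on the assumed correlations. Writing out the unit and its rationale would help a reader, but the number of subjects, the endpoint, the test and what the trial can conclude would all stay the same.

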- 5. Describe how the **subject's privacy will be protected** during the research procedures. **Note**: This is not the same as confidentiality (see the Privacy and Confidentiality web page).
- 6. Be sure to submit **data collection instruments** for review with your e-IRB Application (e.g., measures, questionnaires, interview questions, observational tool, etc.).

Description of Methodology/Study Procedures

Study Design

This study will be conducted at the Beckman Laser Institute outpatient medical clinics. Subjects will be treated as per protocol with a fixed light dose. Biopsies will be performed at the same facilities. Histological analysis will be conducted by the Department of Dermatopathology at UC Irvine. Immunopathology and PCR studies of the biopsied tissue will be conducted by faculty both affiliated with this study and the Massachusettes General Hospital.

Subjects will be recruited through Beckman Laser Institute outpatient medical clinics. Those interested in learning more will be contacted by the clinical research personnel, who will provide each interested person more information on the study and discuss with the person the inclusion and exclusion criteria. If the subject is interested, they will make an appointment to come to Beckman Laser Institute outpatient medical clinics.

At the initial visit, the clinical research personnel will go through the study consent form in detail and complete the necessary informed consent documentation. If the subject is willing, he or she will undergo a brief medical screening visit including a review of medical history, current medications, and review of vital signs (blood pressure, pulse, temperature). During that screening examination, the study personnel will ensure that the subject meets all the inclusion and none of the exclusion criteria. The study personnel will determine the subject's skin phototype. As a result of this initial visit, the subject will be formally enrolled in the study and a clinical research record will be started on the subject. The initial visit will take approximately 30 minutes.

Description of the Intervention

1. Laser Treatment

Within 4 weeks of the initial screening visit, subjects will return for laser treatments.

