doses will be utilized. The typical threshold of pain occurs at about 43° C, so limiting exposures to the subject's discomfort ensures that dermal temperatures will not generally exceed this temperature. At 43° C, the skin would need to be exposed to laser treatment for over an hour to produce skin damage (Yarmolenko PS, Moon EJ, Landon C, Manzoor A, Hochman DW, Viglianti BL, Dewhirst MW. Thresholds for thermal damage to normal tissues: an update. Int J Hyperthermia. 2011;27(4):320-43). In accord with this fact, the proposed study builds in a stopping point for laser treatment during the full one-minute laser treatment based on a study subject's experience of discomfort (e.g., uncomfortable skin hotness or a pins and needles sensation), which precludes damage to the skin by the proposed laser. A water polymer gel will also be applied to the laser-exposed skin in order to prevent excessive heat buildup and subsequent skin damage and discomfort.

Potential Risks of Punch Biopsy

Some of the complications associated with punch biopsy include local bleeding and bruising, pain, infection, allergic reaction to the local anesthetic and scar. These side effects will be minimized by following best medical practice and by using a small size biopsy punch.

Other Risks/Discomforts:

Confidentiality Risks: Since this study involves the use of identifiable information, there is a potential for a breach of confidentiality.

Unknown risks: There may be risks related to the research that we don't know about yet. However, the subject will be informed of any additional risks to which he or she may be exposed, and any changes that are made to the study, as a result of any newly-identified risks.

5. Discuss what steps have been taken and/or will be taken to prevent and minimize any risks/ potential discomforts to subjects (address physical risks as well as other risks such as the potential for a breach of confidentiality). Examples include: designing the study to make use of procedures involving less risk when appropriate; minimizing study procedures by taking advantage of clinical procedures conducted on the subjects; mitigating risks by planning special monitoring or conducting supportive inventions for the study.

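### Stopping at the subject's discomfort is relied on to limit skin heating, yet known reduced sensation and same-day numbing products on the lower back are not screened out: a minor safety improvement

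*Combined protocol and SAP*

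**What the plan says.** Section 7B (Potential Risks of Laser Treatment) places the pain threshold at about 43 °C and concludes that "limiting exposures to the subject's discomfort ensures that dermal temperatures will not generally exceed this temperature". It then describes stopping at the subject's discomfort as a safeguard "which precludes damage to the skin by the proposed laser". The operating rule, under Description of the Intervention (1. Laser Treatment), is that if "an exposure produces discomfort in the subject (a tingling or pinprick sensation or uncomfortable feeling of hotness), the exposure will be terminated". The objective check comes later: "After the completion of each test site, the study personnel will examine the skin surface for signs of damage or alteration".

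Section 4B recognises that products on the back can matter. It excludes "Use of systemic steroids or use of topical steroids on the back within 30 days prior to study" and "Use of tanning solutions on the back within 48 hours prior to study". It does not mention reduced sensation or topical anaesthetics.

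The initial visit is "a brief medical screening visit including a review of medical history, current medications, and review of vital signs". The interval to the first laser exposure is then set: "Within 4 weeks of the initial screening visit, subjects will return for laser treatments".

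Several other protections are stated. Irradiance is capped at 5 W/cm² and each exposure lasts one minute. A water-based gel is applied, irradiance rises in steps, and the site is checked again at 20 to 48 hours. Section 7B also states, before it turns to discomfort, that power and total dose are held well under the published skin-damage threshold.

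**The concern.** A safeguard that depends on feeling heat cannot work in a person who does not feel it. The risk section gives this safeguard strong words, but the eligibility list does not restrict the study to people in whom it can operate. A subject with known numbness of the lower back, or one who applied a numbing cream that morning, meets every written criterion and would simply report no discomfort.

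What is at stake is the safety of that one subject, chiefly during the first-phase escalation. The study is classed as greater than minimal risk and offers subjects no direct benefit, so an inexpensive protection is easy to justify. The primary comparison and its paired t-test are not affected.

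**Working it through.** The plan gives no figure on this point to reproduce. The check sets the relevant texts side by side, with one piece of arithmetic.

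1. **What can end an exposure early.** Three places describe it: the laser-treatment procedure, the heat-damage paragraph in Section 7B, and the closing safety statement in Section 7B. All three name discomfort or pain reported by the subject. None names a skin-temperature reading or a sign seen by the operator. Inspection follows each completed site, and no written rule links its result to stopping.

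2. **What the 43 °C argument needs.** It has three premises: (a) pain starts near 43 °C; (b) the subject reports it and the exposure ends; (c) damage at 43 °C takes more than an hour. Against a one-minute exposure, (c) gives a time margin of more than 60 / 1 = 60-fold. That margin applies only while (b) keeps the skin near 43 °C. If the subject cannot feel heat, (b) fails, and (c) no longer bounds the risk. The documents give no skin temperature reached at any irradiance under the gel, so neither safety nor injury can be derived for that subject by this route.

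3. **Whom Section 4B excludes.** The list covers steroids, tanning solutions, clotting disorders and anticoagulants, mental incompetence, prisoner status, alcohol or drug impairment, immune disorders and immunosuppressants, photosensitivity, and pregnancy. None concerns local sensation. Alcohol or drug impairment is about the person's general state, not numb skin.

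4. **What such a subject would receive in the first phase.** Fluence = irradiance × 60 s:
   - 1 W/cm² × 60 s = 60 J/cm²
   - 2 W/cm² × 60 s = 120 J/cm²
   - 3 W/cm² × 60 s = 180 J/cm²
   - 4 W/cm² × 60 s = 240 J/cm²
   - 5 W/cm² × 60 s = 300 J/cm²

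   With no discomfort reported, all five steps are given. Four inspected lower steps precede the last.

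5. **When the question could be asked.** The only history and medication review is at screening, up to 4 weeks before the tolerance visit. The laser-visit steps repeat the pregnancy test but not this review. A review done on an earlier day cannot detect a product applied on the day. The treatment visit is later still. The protocol gives both a six-month window and an 18-19 week total, so no single interval is put on that gap here.

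6. **Which visit carries the risk.** At the treatment visit everyone receives one exposure at the highest irradiance that all ten tolerated. For a subject who feels nothing, the other nine effectively set that level. The subject's own skin has also already been exposed at that level or above and inspected. The risk there is lower than in the first phase.

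**The case against.** The strongest reply is that discomfort is not the main protection. Section 7B begins with the limit on power and dose relative to the damage threshold, and it later calls the discomfort stop an additional measure. Section 1 says that parameters roughly equivalent to those of the mouse work were tolerated and non-damaging in humans, and Section 3B gives the mouse irradiance as 5 W/cm². Section 7B adds that continuous-wave studies at higher doses reported no immediate thermal damage. On that account a subject who feels nothing is still protected. This largely stands and is why the point is minor. It does not remove the point, because the same section also says that the discomfort stop secures the temperature limit and excludes damage.

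A second reply is that healthy adults aged 18-50, with history and medications reviewed, will seldom have this problem. That is fair, but no criterion tells staff to look for it or what to do if they find it.

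A third reply is that the clearest motive for numbing cream, the biopsy four hours after the laser, arises at the treatment visit, where the hazard is lower and the clinic supplies anaesthesia anyway. This also stands. It weakens the topical-product half more than the reduced-sensation half.

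A reader might infer that 5 W/cm² is unsafe because the only human irradiance figure quoted is 3.84 W/cm². The documents do not support that. The figure comes from a pulsed laser in phototypes V-VI, whereas this study enrols I/II to limit melanin absorption, and Section 1 makes the broader tolerance statement. A reader might also infer that staff would carry on after seeing skin damage. The absence of a written rule does not show this; staff who inspect each site would be expected to act on what they see.

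**Conclusion.** The point holds as a minor safety improvement. The discomfort stop is the only trigger described during the 60 s exposure. Section 7B relies on it in strong terms, and Section 4B admits people in whom it cannot work. The added risk is small, falls on an individual subject and lies mainly in the first-phase escalation.

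The size of the harm cannot be computed. The documents give neither the frequency of reduced lower-back sensation or numbing-product use among eligible subjects nor the chance of injury at any irradiance. Any assumed prevalence would give only the chance of enrolling such a person, not the chance of injury.

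A reader might infer that a subject who feels nothing would push the common second-phase irradiance too high. That does not follow. The level is the highest that all ten tolerate, so it is affected only if that subject would otherwise have been the least tolerant of the ten. The effect is negligible and is not part of this point.

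The conclusion rests on the public protocol text. Visit forms were not available and may already ask the question.

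**What to change.** - **Section 4B:** add the exclusion *Known reduced sensation on the lower back*.
- **Laser-visit procedures:** before the laser at the tolerance visit and again at the treatment visit, ask about reduced sensation and about any topical anaesthetic applied to the lower back that day. If one was applied, defer the visit to another day.

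The question can sit beside the existing pre-laser pregnancy test. Local anaesthesia for the later biopsy is unaffected, and no general deferral for analgesics is proposed.

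The cost is one exclusion line, one deferral rule and a short question at two existing visits, with no extra staff, procedures or subjects. The downside is a rare exclusion or rebooked visit. Up to 15 people may be consented for a target of 10, and the 4-week and six-month windows usually leave room to rebook. A deferred tolerance visit would delay the second phase slightly, because all ten must be tested first.

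The change catches only known or self-reported numbness. It does not add an objective stop during the exposure.
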